APPENDIX I: VEINES QOL

APPENDIX J: Adherence to Conservative Treatment Form

A. PROTOCOL SYNOPSIS

Title:	ACCelerated ThrombolySiS for Post-Thrombotic Syndrome Using the EKOS System (ACCESS PTS)
Design:	A prospective, single arm, multi-center study
Brief Device Description:	The EkoSonic® Endovascular System employs high frequency (2-3MHz), low power ultrasound to facilitate the delivery of therapeutic agents to the intravascular treatment site in the peripheral vasculature.
Purpose:	To evaluate the efficacy of ultrasound accelerated thrombolysis using the EkoSonic® Endovascular System with standard infusion of thrombolytic drug for post-thrombotic syndrome and chronic venous occlusion.
Primary Endpoint:	Clinical effectiveness will be evaluated using the Villalta score at Baseline compared to 30 days Post-EkoSonic® Study Treatment Procedure (EkoSonic® Treatment). Success will be defined by 50% of the subjects achieving at least a 4 point reduction in the Villalta score.
Population:	Subjects with lower extremity deep vein thrombosis (who have failed conservative treatment) objectively diagnosed with imaging \geq 6 months; prior persistent DVT at enrollment evaluation; Villalta score \geq 8. Subjects must be \geq 18 years of age and \leq 75 years of age.
Enrollment:	Up to 200 efficacy evaluable subjects, some with bilateral DVTs. Efficacy evaluable DVT limbs are those (1) with Villalta scores available at both Baseline and 30 days Post-EkoSonic® Treatment and (2) the clot in the affected segment was successfully crossed and received EkoSonic® Treatment.
Clinical Site Locations:	Up to 30 centers within the United States.
Time Course:	Enrollment period of up to 12 months with 365 day follow-up. Subject participation is approximately 12 months.

B. STUDY FLOWCHART and SCHEDULE OF EVENTS

ACCESS PTS Schedule of Assessments	Visit 1 (Within 30 days of treatment) Screening/Baseline	Visit 2 Day 0 Pre-EkoSonic® Treatment	Visit 2 Day 0 Post-EkoSonic® Treatment	Discharge	Visit 3 Day 30 ± 7 days	Visit 4 Day 90 ± 10 days	Visit 5 Day 180 ± 14 days	Visit 6 Day 365 ± 14 days	Early Termination
ACTION									
Informed Consent	X								
Demographics	X								
Medical History & Risk Factors	X								
Inclusions/Exclusion Criteria	X								
Pregnancy test	X								
Physical Exam	X								
Duplex Ultrasound	X ¹		X ²		X	X	X	X	X
Adherence to Conservative Therapy Form	X								
Laboratory Tests	X ³	X ⁴	X ²						
Villalta Scale	X				X	X	X	X	X
CEAP Classification	X				X	X	X	X	X
VCSS	X				X	X	X	X	X
SF-36	X				X	X	X	X	X
VEINES-QOL	X				X	X	X	X	X
Venography		X ⁵	X ⁶						
Leg Circumference	X				X	X	X	X	X
Review of Treatment Compliance & Exercise					X	X	X	X	X
Adverse Events			X	X	X	X	X	X	X
Concomitant medications	X				X	X	X	X	X

¹ Duplex ultrasound within 60 days prior to treatment or venography (Pre- EkoSonic® Treatment) will be performed to confirm persistent chronic DVT causing restrictive flow

²To be performed within 24 hours of the completion of treatment

³Test results may be obtained within 30 days prior to study treatment, unless otherwise specified in the exclusion criteria

⁴To be performed within 24 hours prior to the start of treatment

⁵ To be performed pre- and post-venoplasty

⁶To also be performed post- adjunctive treatment

C. ACRONYMS AND ABBREVIATIONS

AE	Adverse event
aPTT	Activated partial thromboplastin time
CBC	Complete blood count
CEAP	Clinical, Etiologic, Anatomic, Pathophysiological
CFR	Code of Federal Regulations
CFV	Common femoral vein
CPK-MB	Creatine Phosphokinase-MB
CPR	Cardiopulmonary resuscitation
CT	Computed tomography
CTPA	Computed tomography pulmonary angiogram
DIC	Disseminated intravascular coagulation
DVT	Deep vein thrombosis
eCRF	Electronic Case Report Form
ECS	Elastic compression stockings
FTC	Failure-to-Cross
FDA	Food and Drug Administration
GI	Gastrointestinal
ID	Identification
IDDC	Intelligent Drug Delivery Catheter
INR	International normalized ratio
ITT	Intention-to-treat
IVC	Inferior vena cava
MDR	Medical Device Reporting
MRI	Magnetic Resonance Imaging
MRV	Magnetic resonance venography
MSD	MicroSonic Device
PCB	Pneumatic compression boots
PCS	Physical component summary
PE	Pulmonary Embolism
PP	Per protocol
PTS	Post-thrombotic syndrome
PTT	Partial thromboplastin time
QoL	Quality of Life
rt-PA	Recombinant tissue plasminogen activator
SAR	Serious adverse reaction
SAE	Serious adverse event
SF-36	Short Form 36
SPECT	Single positron emission computed tomography
VEINES-QOL	Venous Insufficiency Epidemiological and Economic Study- Quality of Life
VCSS	Venous Clinical Severity Score
VVI	Venous Volumetric Index
VQ	Ventilation-perfusion

1.0 INTRODUCTION

The purpose of this prospective study is to evaluate the efficacy of ultrasound accelerated thrombolysis using the EkoSonic® Endovascular System with standard infusion of thrombolytic drug in subjects who suffer from Post-Thrombotic Syndrome (PTS) as a result of chronic venous occlusion. This study will assess thrombus clearance and vein patency at the conclusion of the EKOS intervention, and will document subject symptoms before and after the EKOS intervention and at 30, 90, 180, and 365 days follow-up. The resulting data will support a journal publication.

Deep vein thrombosis (DVT) is a common problem affecting between 250,000 and 2 million people annually in the US.¹ The most common complication of DVT is PTS, which can affect from 25% to 60% of DVT subjects.² Despite therapeutic anticoagulation and elastic compression stocking (ECS) therapy, a significant proportion of DVT subjects progress to develop post-thrombotic sequelae which lead to significant limitations in their quality of life.^{3,4}

Venous hypertension resulting from chronic obstruction of the vein lumen after DVT is considered to be a key pathophysiological feature of PTS. The goal in treating chronic obstruction is to restore flow in the occluded venous segment, thereby decreasing venous pressures and subsequently, the severity of PTS. Although as yet there are no Level 1 data, it has been shown in a single-center retrospective registry study that recanalization of chronically occlusive DVT can be safely and successfully performed to provide significant improvement in venous flow, and relief of symptoms.⁵

Combined ultrasound/lytic therapy was developed to accelerate thrombolysis and rapidly achieve complete clot lysis while reducing the risk of serious complications such as bleeding. High frequency, low power ultrasound accelerates thrombolysis both *in vitro* and *in vivo*. This idea was pioneered by Kudo and confirmed by other investigators.^{6,7,8,9} Ultrasound temporarily alters the local architecture of the fibrin clot, thereby enhancing its permeability by reducing the diameter of the fibrin strands and increasing the pore size of the fibrin mesh.¹⁰ Ultrasound energy also provides an acoustic pressure gradient to enable transportation of a greater quantity of thrombolytic drug into the clot itself. The resulting faster, more complete clot lysis is due to increased diffusion of the thrombolytic agent into the clot and not mechanical disruption.

The EkoSonic® Endovascular System is an FDA cleared drug delivery catheter that uses ultrasound delivered through the catheter core to speed the delivery of thrombolytic drug into the interstices of the clot and increase the speed of lysis. By making the clot more permeable and pushing the drug into the fibrin mesh, the EkoSonic® Endovascular System has the potential to reduce time to lysis, effect more complete lysis, reduce drug dose and thereby reduce the risk of bleeding complications. In the case of chronic obstruction, it is hypothesized that the effects of ultrasound allow the infused thrombolytic agent to act on any fibrin remaining in retracted, chronic thrombus.

2.0 DEVICE

2.1 Intended use

The EkoSonic® Endovascular System employs ultrasound energy intended to facilitate the controlled and selective infusion of physician-specified fluids, including thrombolytics, into the peripheral vasculature.

2.2 Description

The following is a summary of the EkoSonic® Endovascular System. The Instructions for Use (IFU) is included in Appendix A and is also provided with each system.

The system generates ultrasound waves in the treatment zone of the catheter through the piezoelectric conversion of radiofrequency energy. The ultrasound emanates radially from the treatment zone to improve the dispersion of infused physician-specified fluids, including thrombolytics.

The EkoSonic® Endovascular System consists of two main components:

- EkoSonic® Device
 - Single-use sterile device, consisting of an
 - Intelligent Drug Delivery Catheter (IDDC)
 - MicroSonic Device (MSD)
- EkoSonic® Control System (reusable)

The IDDC is 5.4 French with a 106 cm or 135 cm working length. It includes two luer ports for coolant fluid and thrombolytic delivery and an electrical connector for the thermocouples that monitor the catheter system temperature. Radiopaque markers are located approximately 1 cm proximal and 1 cm distal to the treatment zone. The IDDC central lumen is compatible with a 0.035" guidewire, accepts the MSD and delivers coolant during operation.

The MSD locks to the luer connector on the central lumen of the IDDC aligning the ultrasound-generating segment to the treatment zone of the IDDC. The device uses multiple ultrasound transducers to emit ultrasound energy radially from the long axis of the catheter system.

The EkoSonic® Control System provides electrical power to the piezoelectric elements in the treatment zone of the EkoSonic® Device and monitors operating parameters during operation. The Control System also provides the user interface through the front panel display and keypad.

2.3 Regulatory Status

The EkoSonic® Endovascular System has been cleared by the United States Food and Drug Administration (FDA) for the controlled and selective infusion of physician-specified fluids, including thrombolytics, into the peripheral vasculature and is marketed throughout the United States. In this study, the EkoSonic® Endovascular System is being used in accordance with its cleared indications for use.

The EkoSonic® Endovascular Devices used for this study will be "off the shelf". Therefore, no special labeling or tracking is required for study devices.

3.0 STUDY OBJECTIVES AND STUDY ENDPOINTS

3.1 Primary Objective

Evaluate the safety and efficacy of the EkoSonic® Endovascular System for the treatment of lower extremity DVT in subjects with PTS who have failed conservative treatment.

3.1.1 Primary Clinical Efficacy Endpoint

Clinical efficacy will be evaluated using the Villalta score at Baseline compared to 30 days Post-EkoSonic® Study Treatment Procedure. Study success will be defined by ≥50% of the efficacy evaluable limbs achieving at least a 4 point reduction.

3.1.2 Primary Technical Efficacy Endpoint

Increase in blood flow calculated by time to washout in the affected segments, measured at Baseline and Post-EkoSonic® Study Treatment Procedure. A statistically significant improvement in flow rate will be considered success.

3.2 Secondary Objectives

To further evaluate clinical efficacy, device and procedural safety, and potential quality-of-life improvement.

3.2.1 Secondary Clinical Efficacy Endpoints

1. Occlusive material burden using the Venous Volumetric Index (VVI) Score¹¹, measured at Baseline and Post-EkoSonic® Study Treatment Procedure, both as a continuous measure and as a binary variable for achievement of a ≥ 5 point reduction from Baseline to Post-Procedure.
2. Change in Villalta score from Baseline to 90 days, 180 days, and 365 days Post-EkoSonic® Study Treatment Procedure, both as a continuous measure and as a binary variable for having achieved a ≥ 4 point reduction from Baseline.
3. Absence of re-occlusion at 365 days of the treated segment, as documented by duplex imaging.
4. Change in SF-36 Quality of Life (QoL) and Physical Component Summary (PCS), CEAP classification, VEINES-QOL, and VCSS from Baseline to 30, 90, 180 and 365 days Post-EkoSonic® Study Treatment Procedure.
5. Symptomatic PTS-induced admission to emergency room or unplanned visit to physician office or hospitalization from Post-EkoSonic® Study Treatment Procedure up to 365 days thereafter
6. Time from starting initial thrombolytic infusion to discharge from hospital

3.3 Safety Endpoints

1. Frequency of major bleeding^{12,13} within 72 hours of initiating treatment with the EkoSonic® Endovascular System, as defined by:
 - a. Fatal bleeding, and/or
 - b. Symptomatic bleeding in a critical area or organ, such as intracranial, intraspinal, intraocular, retroperitoneal, intraarticular or pericardial, or intramuscular with compartment syndrome, and/or
 - c. Bleeding causing a fall in hemoglobin level of 20 gL^{-1} (1.24 mmol L^{-1}) or more, or leading to transfusion of two or more units of whole blood or red cells.
2. Rate of symptomatic pulmonary embolism (PE; diagnosed using computed tomography pulmonary angiogram (CTPA), single positron emission computed tomography (SPECT), ventilation-perfusion (VQ), etc.) during hospitalization for study procedure.

4.0 CLINICAL PLAN

Up to 200 efficacy evaluable subjects (see 6.1 for definition), some with bilateral DVT, will be enrolled in the study at up to 30 clinical sites, with a maximum of 30 subjects enrolled at any given site.

This is a prospective, single-arm, multi-center study intended to assess the clinical and imaging outcomes of subjects with chronic lower extremity venous obstruction after DVT and PTS who are treated with thrombolytic infusion using the EkoSonic® Endovascular System. Administration of the Villalta scale must be performed by a trained clinician at each visit. It is preferable that the same clinician performs the scale on an individual subject throughout the study.

Subjects that are diagnosed with a lower extremity DVT by duplex imaging and/or venography at least 6 months previously will be evaluated for inclusion in the study. Eligible subjects will provide written informed consent. Following baseline evaluation, venous access shall be obtained. For the purpose of this study, venous access is considered initiation of EkoSonic® Treatment. If the occlusion cannot be completely traversed by a guide wire or EkoSonic® Device or severe vessel damage has occurred, the subject will be considered as a “failure-to-cross” (FTC). FTC subjects will complete follow-up visits throughout the 12 month endpoint period and undergo the follow-up assessments.

After successful passage of the guide wire, an angioplasty balloon shall be placed and then dilated across the entire occlusive segment to promote enlargement of the channel to allow passage of the EkoSonic® IDDC.

Following successful placement of the IDDC, the MSD will be placed. Ultrasound accelerated EkoSonic® thrombolysis will be initiated with the use of alteplase. Follow-up venographic evaluation shall be performed of the entire affected limb once the EkoSonic® thrombolysis procedure is completed. At the discretion of the Investigator, adjunctive treatments such as angioplasty or stenting can be performed as necessary to enhance venous flow after treatment with the EkoSonic® Endovascular System. Additional venography shall be performed after all adjunctive treatment is completed.

Post-Procedure duplex imaging of the treated venous segments shall be performed within 24 hours of completing the interventional procedure (thrombolysis and any adjunctive therapy). Follow-up evaluation shall occur at 30, 90, 180, and 365 days.

It is anticipated that the clinical study duration will be 24 months including first subject enrollment through to last subject completed or until the study is formally terminated. An individual subject’s participation will be approximately 12 months.

4.1 Study Population

4.1.1 Inclusion Criteria

Subjects must meet the following criteria to be eligible for participation in this clinical trial:

1. Male or female ≥ 18 years of age and ≤ 75 years of age.
2. Proximal DVT (iliac vein, common femoral vein, deep femoral vein, femoral vein) that was objectively diagnosed with duplex imaging and/or venography ≥ 6 months prior to study screening.
3. Persistent chronic DVT causing restrictive flow, as confirmed by imaging, within 60 days prior to the study procedure.
4. Villalta score ≥ 8 for the affected limb within 30 days prior to the study procedure.
5. Medically eligible for treatment with thrombolytic drugs (see alteplase package insert in Appendix B).
6. Informed of the nature of the trial, is willing and has provided written, informed consent as approved by the Institutional Review Board/Ethics Committee (IRB/EC) of the respective investigational site.

7. Failed a minimum of 3 consecutive months of conservative treatment (therapeutic anticoagulation and compression stockings) according to the completed Adherence to Conservative Treatment Form.
8. Agrees to comply with specified follow-up evaluations and to return to the same investigational site where the procedure was performed.

4.1.2 Exclusion Criteria

Subjects with any one of the following shall be excluded from participation in this clinical trial:

1. Treated with mechanical thrombectomy within 2 weeks of the study thrombolysis procedure.
2. Treated with thrombolysis drugs within 48 hours of the study thrombolytic procedure.
3. Life expectancy less than 1 year.
4. Body Mass Index (BMI) >40 kg/m² or per Investigator's discretion subject is able tolerate the procedure and be compliant with post-procedure increased physical activity.
5. No flow in popliteal vein on duplex imaging
6. Isolated iliac vein only thrombus.
7. Thrombus extending \geq 3 cm into the inferior vena cava (IVC). If central venous occlusion, consider computed tomography (CT) or magnetic resonance venography (MRV). For subjects with bilateral DVT, it is recommended that central imaging be performed prior to treatment to evaluate the status of the IVC.
8. Active bleeding, recent (< 3 mo) gastrointestinal (GI) bleeding, active peptic ulcer, severe liver dysfunction, bleeding diathesis.
9. Recent (< 3 mo) internal eye surgery or hemorrhagic retinopathy; recent (< 10 days) major surgery, cataract surgery, trauma, cardiopulmonary resuscitation (CPR), obstetrical delivery, or other invasive procedure.
10. History of stroke or intracranial/intraspinal bleed, tumor, vascular malformation, aneurysm.
11. Active cancer (metastatic, progressive, or treated within the last 6 months). Exception: subjects with non-melanoma primary skin cancers are eligible to participate in the study.
12. Hemoglobin < 9.0 mg/dl within 24 hours prior to the procedure
13. International normalized ratio (INR) \geq 1.5 ng/dl within 24 hours prior to the procedure
14. Platelet count < 100,000 cells/mm³ or >700,000 cells/mm³ within 24 hours prior to the procedure.
15. Creatinine outside the normal range for the treating institution and considered clinically significant by the Investigator.
16. Uncontrolled hypertension, defined as systolic \geq 175 mmHg and a diastolic \geq 110 mmHg.
17. Use of clopidogrel, ticlopidine, or other thienopyridine antiplatelet drug within 7 days of the study procedure.
18. In the judgment of the clinician, the subject is at high risk for catastrophic bleeding.
19. Known allergy, hypersensitivity, or thrombocytopenia from heparin, alteplase (rt-PA), or iodinated contrast except for mild-moderate contrast allergies for which steroid pre-medication can be used.

20. Inability to tolerate the procedure due to acute systemic illness or other comorbidities that in the opinion of the Investigator place the subject at high risk for complications.
21. Subject is pregnant (positive pregnancy test; women of childbearing age must be tested), breast feeding, or planning to become pregnant during the study.
22. Inability to provide informed consent or to comply with study assessments (e.g. due to cognitive impairment or geographic distance).

NOTE: Subjects excluded because of time-related exclusion criteria may be re-evaluated for inclusion in the study when the proper time interval has passed, i.e., >10 days after surgery, >3 months after GI bleed.

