4.2 Procedures

4.2.1 Screening/Baseline Evaluation

All subjects presenting for evaluation and treatment of chronic lower extremity venous obstruction after DVT will be considered for the study. The date of evaluation will be captured along with whether the subject was included in the study or the reason for exclusion.

All subjects that meet the study's inclusion criteria and do not meet any exclusion criteria are eligible for this study. Subject Informed Consent shall be obtained prior to performing study related procedures. No subject will be enrolled without signing the Subject Informed Consent. A subject who was screened but was not eligible for the trial will be considered a screen failure. The site will maintain a log that includes each screen failure subject along with the reason for study exclusion.

EKOS will ensure that the confidentiality of subjects' identification is maintained and medical records are protected. A unique subject identification (ID) will be assigned by the data collection system for each subject enrolled in the clinical study. Subject records may be reviewed by EKOS representatives to verify the quality of the reported data; however, confidentiality will be maintained.

The following assessments shall be performed within 60 days prior to the study procedure:

- Imaging (duplex ultrasound or venography) to confirm presence of chronic DVT causing restrictive flow as well as some degree of flow in the popliteal vein. A subject who does not meet the imaging criteria will be considered a screen failure.

The following assessments shall be performed within 30 days prior to the study procedure:

- Demographics
- Pregnancy test for women of child bearing potential
- Medical history and risk factors, including any coagulopathies
- Physical exam with documentation of PTS signs and symptoms
- Villalta scale (both legs)
- CEAP classification (both legs)
- VCSS (both legs)
- SF-36
- VEINES-QOL
- Laboratory tests: hemoglobin, INR, and platelet count must be obtained within 24 hours prior to the EkoSonic® Treatment procedure in order to confirm eligibility.
- Leg circumference (both legs)

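### Exclusion criterion 4 is inverted: as written, it excludes subjects whom the investigator judges able to tolerate the procedure and keep up the activity

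*Protocol*

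**What the plan says.** The lead-in to Protocol section 4.1.2 sets the rule for the whole list: "Subjects with any one of the following shall be excluded from participation in this clinical trial". Section 4.2.1 repeats it from the other side: subjects who satisfy the inclusion criteria and "do not meet any exclusion criteria are eligible for this study".

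Item 4 has two limbs joined by *or*. The first is BMI above 40 kg/m². The second is that, at the investigator's "discretion subject is able tolerate the procedure and be compliant with post-procedure increased physical activity".

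Other items in the list bear on how item 4 should be read:

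- Item 20 excludes for "Inability to tolerate the procedure due to acute systemic illness or other comorbidities", where the investigator considers that this puts the subject at high risk.
- Item 22 excludes for inability to consent or to comply with assessments.
- Items 11 and 19 contain carve-outs and mark them openly: "Exception: subjects with non-melanoma primary skin cancers are eligible to participate in the study" and "except for mild-moderate contrast allergies for which steroid pre-medication can be used".

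Section 4.2.5 asks that subjects be encouraged to walk and exercise after discharge. BMI is mentioned nowhere else in the protocol.

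**The concern.** An item in an exclusion list should describe a reason to keep someone out. The second limb of item 4 describes a reason to let someone in. Taken with the lead-in and section 4.2.1, it disqualifies a subject for being fit for the procedure and for the activity that the protocol wants afterwards.

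No investigator would apply that literally, so each site has to correct the sentence for itself, and more than one correction is possible. The issue is whether a subject with BMI above 40 who is judged able may be enrolled. One site could refuse such a subject and another could enrol one, each believing that it follows the protocol. Section 10.3 requires deviations to be recorded and reported, and a monitor could not tell from this text whether such an enrolment is a deviation.

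**Working it through.** There is no plan figure to reproduce. The check is one of logic.

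**Inputs.** Any one item excludes (4.1.2 lead-in). Only subjects with no exclusion are eligible (4.2.1). Item 4 is: BMI above 40, *or* judged able. Here *able* means able both to tolerate the procedure and to comply with increased activity, so *not able* means failing at least one of the two.

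**Three readings of item 4.**

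- As written: excluded if BMI >40 or able.
- Repair A (*or is unable*): excluded if BMI >40 or not able.
- Repair B (*unless able*): excluded if BMI >40 and not able.

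| Group | As written | Repair A | Repair B |
|---|---|---|---|
| BMI >40, able | excluded | excluded | admitted |
| BMI >40, not able | excluded | excluded | excluded |
| BMI ≤40, able | excluded | admitted | admitted |
| BMI ≤40, not able | admitted | excluded | admitted |

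**Results.**

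1. The literal text excludes 3 of the 4 groups and admits 1: BMI ≤40, not able.
2. BMI ≤40, able is excluded literally and admitted by both repairs. In that group the text is wrong under any sensible reading.
3. Repair A also admits 1 of 4, but the opposite one: BMI ≤40, able.
4. The literal text and repair A agree on both BMI >40 groups. Repair B departs from them in 1 of those 2: BMI >40, able.
5. The repairs also differ for BMI ≤40, not able. Item 20 already removes those who cannot tolerate the procedure because of illness or comorbidity. What remains there is mainly expected non-compliance with activity.

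**Which repair does the text support?** Repair A has more behind it. The connecting word is *or*, the lead-in says that any one item excludes, and where this list means an exception (items 11 and 19) it says so. Repair B remains plausible, because investigator discretion combined with *is able* reads like a waiver of a BMI limit. With BMI mentioned nowhere else, a site has nothing further with which to settle the matter.

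**The case against.** The strongest reply accepts the drafting error and disputes its consequence.

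- The intended direction is obvious from item 20 and from the exercise advice in section 4.2.5. By the November 2016 change, an interim analysis planned at 35 evaluable segments had been performed (section 6.2.5), so sites were enrolling and cannot have applied item 4 literally.
- The ambiguity is confined to BMI >40 judged able, and arises only where a site adopts the less supported waiver reading. Nothing shows that this happened.
- The four groups are logical combinations without frequencies, so three of four does not measure impact.
- No inference is touched.
- BMI is not named in the schedule of assessments or the baseline list, so a retrospective listing may be harder than it sounds.

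Much of this stands. The count of groups describes the rule and does not estimate how many subjects are affected; the number is unknown and no statistical quantity moves. But enrolment having gone ahead shows only that sites departed from the literal words, not that they all departed in the same way. The point about retrieving BMI does not hold: section 10.2 requires source records sufficient to verify the entry criteria, and BMI >40 is one of them.

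**Conclusion.** The concern holds. Item 4 is wrong as written: it excludes BMI ≤40 subjects judged able, contradicts the direction of items 20 and 22, and is corrected nowhere else in the protocol. The practical consequence is narrower than the literal reading suggests. It lies chiefly in how up to 30 sites treat subjects with BMI >40 judged able, who are refused under the better supported repair and may be enrolled under the other. Subjects with BMI >40 judged not able are excluded either way.

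This should be fixed because it is an operative eligibility rule, but it does not threaten the analysis: endpoints, analysis sets, power and the success rule are unaffected. The conclusion assumes that item 4 was meant to keep out subjects unfit for the procedure or the activity, as items 20 and 22 and section 4.2.5 indicate. The documents do not say how many subjects are involved or how sites have read the item.

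**What to change.** Amend item 4 to read:

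> BMI >40 kg/m², or, in the Investigator's judgment, the subject is unable to tolerate the procedure or to comply with increased physical activity afterwards.

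Only if the sponsor meant the BMI limit to be waivable, use instead:

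> BMI >40 kg/m², unless the Investigator judges the subject able to tolerate the procedure and to comply with increased physical activity afterwards.

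Tell all sites which meaning applies. Because enrolment is already past the interim analysis, also list any enrolled subjects with BMI >40 and any refused under item 4. The refusals can be found because section 4.2.1 already provides that "The site will maintain a log that includes each screen failure subject along with the reason for study exclusion".

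The cost is one line in an amendment, one site notice, and one listing from existing enrolment, source and screen-failure records.
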